# 4.5.5.5. Immunogenicity

## 4.5.5.5.1. Definitions of Sample ADA Status

At a high level, an individual sample is potentially examined multiple times, in a hierarchical procedure, to produce a sample ADA assay result, and potentially, multiple cross-reactive antibodies assay results, and multiple NAb assay results. The cut points used, the drug tolerance of each assay, and the possible values of titers are operating characteristics of the assay.

Figure GPHZ.4.1 details a flow chart that reflects the multi-tiered testing approach.

Abbreviations: ADA = anti-drug antibodies; CP = cut point; GIPR = the glucose-dependent insulinotropic polypeptide receptor; GLP-1R = glucagon-like peptide-1 receptor; LY = LY3298176 (tirzepatide); NAb = neutralizing antibodies; nGIP = native glucose-dependent insulinotropic polypeptide; nGLP-1 = native glucagon-like peptide-1

Figure GPHZ.4.1. Flowchart of immunogenicity multitiered testing approach.

Table GPHZ.4.7 outlines results as reported from Tier 2a of the multi-tiered testing approach. Tier 4 results are reported similarly.

Table GPHZ.4.7. Sample Anti-Drug Antibodies (ADA) Assay Results

Sample Laboratory Result	Explanation
Detected	ADA are detected and confirmed.
Not Detected	The raw result as reported from the laboratory indicates not detected.  The clinical interpretation of such results depends on other factors (see Table GPHZ.4.8).
NO TEST, QNS, etc	Sample exists but was unevaluable by the assay.

Abbreviations: ADA = anti-drug antibodies; QNS = quantity not sufficient.

It can be the case that the presence of high concentrations of tirzepatide will affect immunoassays, and conversely high levels of antibodies may affect the measurement of tirzepatide concentration. Thus, a tirzepatide drug concentration, assessed from a sample drawn at the same time as the ADA sample, plays a key role in clinical interpretation of a sample when the laboratory result is Not Detected (see Table GPHZ.4.8).

Table GPHZ.4.8. Sample Clinical ADA Interpretation Results

Sample Clinical Interpretation	Explanation	
ADA Present	ADA assay result is Detected	
ADA Not Present	ADA assay result is Not Detected and simultaneous drug concentration is at a level that has been demonstrated to not interfere in the ADA detection method (i.e., drug concentration is below the assay's drug tolerance level). For participants receiving placebo, drug concentration is not assessed and is assumed to be below the assay's drug tolerance level.	
	If drug concentration was planned but is not available for a treatment-period sample, a Not Detected sample will be declared ADA Not present.	
ADA Inconclusive	ADA assay result is Not Detected but drug concentration in the sample is	
	≥ the assay's drug tolerance level, which may cause interference in the	
	ADA detection method.	

Abbreviations: ADA = anti-drug antibodies.

All ADA present samples will be evaluated for cross-reactivity to native GIP (Tier 2b), cross-reactivity to native GLP-1 (Tier 2c), NAb LY (tirzepatide) on GIPR (Tier 4a), and NAb LY (tirzepatide) on GLP-1R (Tier 4b). If cross-reactivity ADA against native GIP is detected, the *in silico* assessment for cross-reactivity NAb against native GIP is evaluated, and if cross-reactivity ADA against GLP-1 is detected, the *in silico* assessment for cross-reactivity NAb against native GLP-1 is evaluated (Figure GPHZ.4.1).

Similar terminology to Table GPHZ.4.8 applies for each type of cross-reactive and NAb assay. Importantly, each of these is a distinct assay and, in general, has different assay operating characteristics.

The following are considered inconclusive for the NAb result:

- NAb LY on GIPR: if NAb result is not detected, and PK concentration is ≥ drug tolerance limit of the NAb LY on GIPR assay
- NAb LY on GLP-1R: if NAb result is not detected, and PK concentration is ≥ drug tolerance limit of the NAb LY on GLP-1R assay

An *in silico* method utilizing results from Tiers 2b and 2c, Tiers 4a and 4b, and tirzepatide concentrations is used to determine cross-reactive NAb against native GIP and GLP-1. The *in silico* method is outlined in the following table (Table GPHZ.4.9).

Table GPHZ.4.9. In Silico Classification for Cross-Reactive NAb

In Silico Classification	Cross-reactive Binding ADA Result	NAb Result	Circulating Tirzepatide Level (ng/mL)	In Silico Cross-reactive NAb Interpretation
Cross-reactive NAb to nGIP	Tier 2b: "Not Detected"	Tier 4a: "Not Detected" or "Detected" or N/A or Missing	Any Value or Missing	Not Present
	Tier 2b: "Detected"	Tier 4a: "Not Detected"	< drug tolerance limit of Tier 4a assay	Not Present
	Tier 2b: "Detected"	Tier 4a: "Not Detected"	≥ drug tolerance limit of Tier 4a assay	Inconclusive
	Tier 2b: "Detected"	Tier 4a: "Detected"	< drug tolerance limit of Tier 4a assay	Present
	Tier 2b: "Detected"	Tier 4a: "Detected"	≥ drug tolerance limit of Tier 4a assay	Present
Cross-reactive NAb to nGLP-1	Tier 2c: "Not Detected"	Tier 4b: "Not Detected" or "Detected" or NA or Missing	Any Value or Missing	Not Present
	Tier 2c: "Detected"	Tier 4b: "Not Detected"	< drug tolerance limit of Tier 4b assay	Not Present
	Tier 2c: "Detected"	Tier 4b: "Not Detected"	≥ drug tolerance limit of Tier 4b assay	Inconclusive
	Tier 2c: "Detected"	Tier 4b: "Detected"	< drug tolerance limit of Tier 4b assay	Present
	Tier 2c: "Detected"	Tier 4b: "Detected"	≥ drug tolerance limit of Tier 4b assay	Present

Abbreviations: ADA = antidrug antibodies; GIP = glucose-dependent insulinotropic polypeptide; GLP-1 = glucagon-like peptide-1; NAb = neutralizing antibodies; nGIP = native glucose-dependent insulinotropic polypeptide; nGLP-1 = native glucagon-like peptide-1; Tier 2b = cross-reactive ADA to nGIP; Tier 2c = cross-reactive ADA to nGLP-1; Tier 4a = NAb LY (tirzepatide) on GIP receptor; Tier 4b = NAb LY (tirzepatide) on GLP-1 receptor.

Note that, in the case of an ADA Inconclusive sample, each of the NAb and Cross-Reactive NAb assay results is taken to be Inconclusive.

Note also that any reference to an assay cut point and/or drug tolerance is population specific, and is subject to modification to study-specific parameters per regulatory guidance.

# 4.5.5.5.2. Definitions of Immunogenicity Assessment Periods

Immunogenicity Baseline Observations: Baseline period for immunogenicity assessment for each participant includes all observations up to baseline visit. In instances where multiple baseline observations are collected, to determine participant ADA status the last non-missing immunogenicity assessment up to first administration of study intervention is used to determine treatment-emergent status (see below).

Immunogenicity Postbaseline Period Observations: Postbaseline period observations for each participant include all observations after the first administration of study drug. There are 2 different periods listed below:

- The planned treatment period is defined as from the first dose of treatment to end of the treatment period.
- The entire postbaseline period is defined as from the first dose of treatment to the end of safety follow-up visit or date of study withdrawal.

# 4.5.5.3. Definitions of Participant ADA Status

Treatment-emergent (TE) ADA-evaluable participants: a participant with a nonmissing baseline ADA result and at least 1 nonmissing postbaseline ADA result.

Treatment-emergent ADA unevaluable participant: any participant who does not meet the evaluable criteria.

Baseline ADA Present (preexisting antibody): ADA detected in a sample collected up to the first dose date and time.

Baseline ADA Not Present: ADA is not detected, and the corresponding tirzepatide PK concentration is missing or below the drug tolerance limit in a sample collected up to the first dose date and time.

TE ADA positive (TE ADA+) participant: A participant who is evaluable for TE ADA is TE ADA+ if either of the following holds:

- The participant has baseline status of ADA Not Present and at least 1 postbaseline status of ADA Present with titer  $\geq 2 \times$  MRD of the ADA assay.
- The participant has baseline and postbaseline status of ADA Present, with the postbaseline titer being 2 dilutions (4-fold) greater than the baseline titer. That is, the participant has baseline (B) status of ADA Present, with titer 1:B, and at least 1 postbaseline (P) status of ADA Present, with titer 1:P, with P/B ≥4.

As shown in Figure GPHZ.4.1, a titer is expected when ADA assay result is detected. On occasion, the corresponding assay cannot be performed, in which case a titer value will be imputed for the purpose of TE ADA determination. A baseline sample with detected ADA and

no titer is imputed to be the MRD (1:10) and a postbaseline sample with ADA detected and no titer is imputed to be one dilution above the MRD (1:20).

TE ADA-Inconclusive participant: a TE ADA-evaluable participant is TE ADA Inconclusive if ≥20% of the participant's postbaseline samples are ADA Inconclusive and all remaining postbaseline samples are ADA Not Present.

TE ADA-negative (TE ADA-) participant: a TE ADA-evaluable participant is TE ADA- when the participant is not TE ADA+ and not TE ADA Inconclusive.

For each NAb assay, the following is defined:

NAb-positive (NAb+) participant: a participant who is TE ADA+ and has a Nab+ sample in the postbaseline period.

NAb-Inconclusive participant: a participant who is TE ADA+, is not NAb+, and all samples that have TE ADA+ titer have a NAb-Inconclusive sample result.

NAb-negative (NAb-) participant: a participant is neither NAb+ or NAb inconclusive.

Unless specified otherwise, the above-mentioned definitions of NAb are applicable to all NAb analyses, including cross-reactive NAb analyses, and cross-reactive antibodies.

# 4.5.5.4. Analyses to be Performed

The count and proportion of participants who are TE ADA+ will be tabulated by treatment group, where proportions are relative to the number of TE ADA-evaluable participants, as defined above. The tabulation will include the count and proportion of participants with ADA Present at baseline and the count and proportion of TE ADA+ participants exhibiting each type of cross-reactive antibodies and NAb. This analysis will be performed for

- the planned treatment period, and
- the entire postbaseline period including safety follow-up.

The *in silico* classification for cross-reactive NAb will be summarized.

A summary will be provided of the count and percentage of tirzepatide-treated participants experiencing specific TEAE (see Table GPHZ.4.10) by TE ADA status (TE ADA+, TE ADA, TE ADA Inconclusive) during the planned treatment period.

Table	GPHZ.4.10.	Adverse Events	for	Analysis with	Immunogenicity Results

TEAE category	Criteria	
Hypersensitivity reactions	Anaphylaxis SMQ (narrow or algorithm)	
	Hypersensitivity SMQ (narrow)	
	Angioedema SMQ (narrow)	
	Severe Cutaneous Adverse Reaction SMQ (narrow)	
	Vasculitis SMQ (narrow)	
Injection site reactions	Injection site reaction HLT	
	Infusion site reaction HLT	
	Administration site reaction HLT	

Abbreviations: HLT = high-level term; MedDRA = Medical Dictionary for Regulatory Activity; SMQ = standardized MedDRA query; TEAE = treatment-emergent adverse event.

A listing will be provided for all participants who had ADA Present at any time (including baseline) or had any specific TEAE (see Table GPHZ.4.10). This listing includes a time course of ADA (clinical interpretation result plus flags for samples meeting TE ADA+ criteria and for samples with cross-reactive antibodies and NAb present) along with the TEAE.

Cases of TE ADA that are associated with TEAEs of either severe/serious hypersensitivity or ISRs will be classified as AESIs.

Additional immunogenicity analyses as determined later may be presented. The relationship between antibody titers, the PK parameters, and PD response to tirzepatide may also be assessed.

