- g Calculated by the central laboratory and result provided to investigative sites.
- In the event of systemic drug hypersensitivity reactions (immediate or nonimmediate), additional blood samples will be collected including ADA, PK, and exploratory biomarker samples. PK samples for immunogenicity must be taken prior to drug administration.
- ⁱ Assayed by a Lilly-designated laboratory.
- creatine kinase MB (CK-MB) is to be assayed if creatine kinase result >1000 U/L.

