10.3. Appendix 3: Laboratory Assessments for Hypersensitivity Events

- Laboratory assessments should be performed if the participant experiences generalized urticaria or if anaphylaxis is suspected.
- Collect sample after the participant has been stabilized, and within 1 to 2 hours of the event; however, samples may be obtained as late as 12 hours after the event as analytes can remain altered for an extended period of time. Record the time at which the sample was collected.
- Obtain a follow-up sample at the next regularly scheduled visit or after 4 weeks, whichever is later.

The table below summarizes the laboratory parameters that will be evaluated. These laboratory tests are bundled in the hypersensitivity laboratory testing kit.

Clinical Laboratory Tests for Hypersensitivity Events

Hypersensitivity Tests	Notes	
	Selected test may be obtained in the event of anaphylaxis or systemic allergic/hypersensitivity reactions.	
Tirzepatide ADAs (immunogenicity/ADA)	Assayed by Lilly-designated laboratory. Results will not be provided to the investigative sites.	
Tirzepatide concentrations (PK)	Assayed by Lilly-designated laboratory. Results will not be provided to the investigative sites.	
Tryptase	Assayed by Lilly-designated laboratory. Results will not be provided to the investigative sites.	
	Note : If a tryptase sample is obtained more than 2 hours after the event (that is, within 2 to 12 hours), or is not obtained because more than 12 hours have lapsed since the event, obtain urine sample for N-methylhistamine testing. Note that for tryptase serum samples obtained within 2 to 12 hours of the event, urine N-methylhistamine testing is performed in addition to tryptase testing. Collect the first void urine following the event. Obtain a follow-up urine for N-methylhistamine testing at the next regularly scheduled visit or after 4 weeks, whichever is later.	
N-methylhistamine	Assayed by Lilly-designated laboratory. Results will not be provided to the investigative sites.	
Drug-specific IgE	Will be performed if a validated assay is available.	
	Assayed by Lilly-designated laboratory. Results will not be provided to the investigative sites.	
Basophil activation test	Will be performed if a validated assay is available.	
	Assayed by Lilly-designated laboratory. Results will not be provided to the investigative sites.	

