10.4.7.7. Injection Site Reactions

Symptoms of a local injection site reaction may include erythema, induration, pain, pruritus, and edema. If an injection site event is reported, the AE will be recorded, and additional data will be provided to the sponsor in the Injection Site Reaction eCRF.

At the time of AE occurrence, samples will be collected for measurement of tirzepatide ADA and tirzepatide concentrations.

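### ADA samples triggered by injection-site and some hypersensitivity reactions count towards TE ADA status, which tilts the planned table of those same reactions by TE ADA status towards an association

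*SAP*

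**What the plan says.** **Sampling.** The Schedule of Activities (Protocol Section 1.3) places on-treatment immunogenicity samples at Weeks 4, 12, 24, 52 and 72 (Table 2), with further ones at the early-discontinuation (ED) visit and at Visit 801 (Table 3). Reactions add to these.

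- Injection-site reactions, Protocol 10.4.7.7: "At the time of AE occurrence, samples will be collected for measurement of tirzepatide ADA and tirzepatide concentrations". No severity threshold is set, and no limit on repeat samples.
- Systemic drug hypersensitivity, footnote in Protocol Appendix 2 (Section 10.2): "additional blood samples will be collected including ADA, PK, and exploratory biomarker samples".
- Protocol Appendix 3 (Section 10.3) has a narrower trigger: "Laboratory assessments should be performed if the participant experiences generalized urticaria or if anaphylaxis is suspected". Its list of tests, which includes ADA, is permissive: "Selected test may be obtained in the event of anaphylaxis or systemic allergic/hypersensitivity reactions". It adds: "Obtain a follow-up sample at the next regularly scheduled visit or after 4 weeks, whichever is later".

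**Classification.** SAP 4.5.5.5.2 states: "Postbaseline period observations for each participant include all observations after the first administration of study drug". Under the SAP heading Definitions of Participant ADA Status, a participant without ADA at baseline becomes TE ADA+ with "at least 1 postbaseline status of ADA Present with titer" of at least twice the minimum required dilution. A participant with ADA at baseline needs at least one post-baseline titer four or more times the baseline titer. The Inconclusive class is share-based: at least 20% of post-baseline samples are Inconclusive and all the others are ADA Not Present.

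**Use.** Under Analyses to be Performed, the SAP summarizes the count and "percentage of tirzepatide-treated participants experiencing specific TEAE (see Table GPHZ.4.10) by TE ADA status" for the planned treatment period. Table GPHZ.4.10 defines the reactions by five hypersensitivity-type SMQs and three site-reaction high-level terms. No test is stated. A listing with each participant's ADA time course is also planned, and TE ADA cases associated with severe/serious hypersensitivity or injection-site reactions become AESIs.

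Nothing in Section 4.5.5.5 separates scheduled from unscheduled samples. Table GPHZ.4.1 does so for laboratory tests, vital signs and ECGs, and its footnote refers immunogenicity to Section 4.5.5.5.

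**The concern.** The outcome in the table changes how often the classifying variable is measured. A participant with an injection-site reaction is tested for ADA once more than an otherwise identical participant without one. Because a single qualifying sample is enough, the extra test can only raise the chance of being TE ADA+ or leave it unchanged. Some participants with reactions will then be counted as TE ADA+ only because the reaction prompted a test.

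At stake is how the trial reads the link between antibodies and allergic or local reactions. Part of any excess of reactions among TE ADA+ participants could come from unequal testing, and the table as planned gives no way to tell how much.

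**Working it through.** The documents state no ADA rate and no figure for this table, so there is nothing to reproduce. Each calculation below assumes that reactions are unrelated to ADA.

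**Inputs from the documents:** five scheduled on-treatment samples; at least one qualifying sample for TE ADA+; one extra sample per injection-site reaction; 2 × 87 = 174 tirzepatide participants (Protocol 9.2).

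**Assumed:** the chance *p* that a sample qualifies, the duration of ADA, and a 10% reaction rate.

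**1. Independent samples.** With *m* samples, P(TE ADA+) = 1 − (1 − *p*)^*m*. Compare *m* = 5 (no reaction) with *m* = 6 (one extra).

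| *p* | 5 samples | 6 samples | Odds ratio |
|---|---|---|---|
| 0.02 | 9.6% | 11.4% | 1.21 |
| 0.05 | 22.6% | 26.5% | 1.23 |
| 0.10 | 41.0% | 46.9% | 1.27 |
| 0.20 | 67.2% | 73.8% | 1.37 |

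At *p* = 0.10 the odds ratio is (0.4686/0.5314) / (0.4095/0.5905) = 1.27. Two extra samples at *p* = 0.10 give 52.2% and an odds ratio of 1.57.

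**2. What the table would show** (*p* = 0.10, one extra sample, true reaction rate 10% in everyone):

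- TE ADA+: 0.1 × 0.4686 / (0.1 × 0.4686 + 0.9 × 0.4095) = 11.3%
- not TE ADA+: 0.1 × 0.5314 / (0.1 × 0.5314 + 0.9 × 0.5905) = 9.1%

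**3. Few scheduled samples.** With one scheduled sample and one extra at *p* = 0.10, TE ADA+ goes from 10% to 19%: (0.19/0.81) / (0.10/0.90) = 2.11.

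**4. ADA that persists.** Consecutive samples are unlikely to be independent, so a simulation (500,000 participants per setting) let ADA start uniformly over Weeks 1 to 60 in 30%, 50% or 70% of participants and last an exponentially distributed time. Scheduled draws were at Weeks 4, 12, 24, 52 and 72. The reaction fell at random either early (Weeks 0 to 20) or over all 72 weeks. With one extra sample:

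| Mean ADA duration | Odds ratio |
|---|---|
| 4 weeks | 1.09 to 1.18 |
| 12 weeks | 1.03 to 1.12 |
| 24 weeks | 1.02 to 1.09 |
| persists to Week 72 | 1.00 |

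In the last row a scheduled draw always finds what the extra draw would find.

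**5. Headcount.** 10% of 174 is about 17 participants with a reaction. At *p* = 0.10 with independent samples, 17.4 × (0.4686 − 0.4095) ≈ 1.0 is reclassified by one extra sample each, and 17.4 × (0.5217 − 0.4095) ≈ 2.0 by two.

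**6. Inconclusive class.** One Inconclusive sample of five is 20% (Inconclusive). An extra Not Present sample makes it 1/6 = 16.7%, and the participant becomes TE ADA−. Conversely, with three scheduled Not Present samples, an extra Inconclusive one makes 1/4 = 25% and moves the participant from TE ADA− to Inconclusive. The number of samples matters, but the direction is not fixed.

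**7. Scheduled samples only.** If status uses the five scheduled samples for every completer, P(TE ADA+) is the same with and without a reaction, so the built-in odds ratio is 1.00.

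**The case against.** The strongest reply is that the tilt is small, the table is only descriptive, and the listing already lets a reader see through it. The listing shows the ADA time course beside the reaction and marks the samples that meet the TE ADA+ criteria. For safety, moreover, a sample taken at the reaction may be the most informative one; discarding it could label a participant with transient ADA at the event as TE ADA−.

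Much of this stands. The effect is about one or two participants under the assumptions above, and no inferential claim depends on the table. The point about event-time samples is a good reason not to replace the all-samples status. But a listing does not correct the percentages in a table, and the SAP specifies no flag for unscheduled samples.

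A reader might go further than the documents allow in three ways:

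- **That every reaction in the table brings an extra sample.** This holds for injection-site reactions. For hypersensitivity the triggers are systemic reactions, or generalized urticaria or suspected anaphylaxis, partly in permissive wording. Table GPHZ.4.10 covers five SMQs, so some counted events may bring no extra sample. The follow-up sample may also coincide with a scheduled draw.
- **That the table must show an association.** Only the direction of the push on TE ADA+ is built in. Its size depends on how transient ADA is, and it is zero if ADA persists to a scheduled draw.
- **That the Inconclusive rule is distorted in the same direction.** It can move participants either way.

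**Conclusion.** The point holds as a bias towards an association, of modest and unknown size. The extra sampling, the all-observations rule and the one-sample rule are all in the documents, and Section 4.5.5.5 has no safeguard. It applies fully to injection-site reactions and partly to hypersensitivity.

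For a completer with one extra sample, the plausible built-in odds ratio runs from 1.00 to about 1.4, and is nearer 1 the longer ADA lasts. It is larger for participants with few scheduled samples or with repeated reactions. All these figures rest on assumed ADA rates, ADA durations and a 10% reaction rate. The primary and secondary efficacy analyses are unaffected.

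The table should not be read as the plan's only view of antibodies and reactions, since the listing and the AESI rule also address them.

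**What to change.** In SAP Section 4.5.5.5, add a second version of the table of reactions by TE ADA status. In it, derive TE ADA, NAb and cross-reactive status only from protocol-scheduled treatment-period samples: Weeks 4, 12, 24, 52 and 72, and the scheduled ED sample. Show it beside the all-samples table. In the planned listing, flag event-driven samples as unscheduled.

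Keep all samples for overall TE ADA incidence and for the AESI classification. The ED sample must be included: a participant who leaves before Week 4 might otherwise have no post-baseline result from the treatment period and drop out of the evaluable group for this table.

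The cost is one derivation flag and one more descriptive table. The scheduled-only version may miss transient ADA present only at the event, which is why both versions are shown. It removes the event-triggered part of the imbalance but does not equalize the number of scheduled samples between completers and participants who leave early.
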